2.1.2 Intent-to-Treat analysis set

The Intent-to-Treat (ITT) analysis set will include all randomized patients. ITT patients will be analyzed in accordance to their planned treatment group. This set will be used for listings and summaries of demographic and baseline characteristics.

2.1.3 Full analysis set

The Full analysis set (FAS) will consist of all randomized patients who receive at least one dose of randomized study medication. Full analysis set patients will be analyzed in accordance to

their planned treatment group. This set will be used for listings and summaries of non-HbA1c efficacy data.

2.1.4 Evaluable analysis set

The Evaluable analysis set will consist of all randomized patients who received at least 1 dose of randomized study medication and have a baseline and at least 1 post-baseline HbA1c assessment. Evaluable patients will be analyzed in accordance to their planned treatment group. This set will be used for listings and summaries of HbA1c efficacy data.

2.1.5 Safety analysis set

The Safety analysis set consists of all patients who received at least 1 dose of randomized study medication.

Patients will be analyzed and presented in accordance to the actual treatment received, regardless of planned treatment assignment. If a patient receives at least one dose of exenatide treatment during the assessment period, they will be analyzed and presented in accordance with the actual exenatide treatment received no matter what arm they were randomized to. If a patient randomized to the placebo arm receives exenatide at doses of both 5 µg twice daily and 10 µg twice daily, they will be analyzed and presented in the 10 µg twice daily treatment group.

This set will be used for listings and summaries of safety data during the treatment period.

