The main risks associated with exenatide treatment include mild or moderate nausea (for approximately half of treated patients) that is more frequent at the initiation of therapy and an increased risk of mild or moderate hypoglycemia if the patient is also using an SU. Approximately 43% of adult patients taking exenatide exhibit a temporal rise in antibodies to exenatide, which are mostly of low titer ( $< 1/125$ ). In about 3% of all patients in the three 30-week registration trials, the formation of antibodies to exenatide at high titers was associated with failure to achieve adequate improvement in glycemic control. Postmarketing reports have linked exenatide use to acute pancreatitis and to altered renal function. As it is eliminated by the kidneys, exenatide should not be used by patients with severe renal impairment or end-stage renal disease.

Type 2 diabetes accounts for approximately 45% of all new cases of diabetes in adolescents (Dietz and Robinson 2005). Evidence has shown that a diagnosis of type 2 diabetes in childhood, coupled with inadequate glycemic control, increases the risk of early mortality as well as early end organ damage (Cavallo 2006). The current study will investigate the safety and efficacy of exenatide in the treatment of type 2 diabetes in adolescents, and will provide important information on the potential clinical use of exenatide in that population.

More detailed information about the known benefits and risks of exenatide may be found in the Investigator's Brochure (IB).

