1.2 Study design

This is a multicenter, double-blind, placebo-controlled, randomized, parallel, 3-arm trial. Approximately 195 adolescents, ages 10 to 17 years inclusive, with type 2 diabetes will be enrolled. The number of patients aged 17 years of age will be limited to no more than 10% of patients in each treatment arm. Patients will be naïve to antidiabetic agents, or they will be receiving oral treatment with metformin, an SU, or a combination of metformin and an SU at the time of enrolment. Randomization will be stratified by the patient’s background diabetes therapy and screening HbA1c. The study will commence with a 1-week, single-blind, injectable placebo lead-in period before patients are randomly assigned to add injectable exenatide or injectable placebo to their existing diabetes treatment. Patients will be randomly assigned to 1 of 3 treatment arms: exenatide 5 µg twice daily, exenatide 10 µg twice daily, or placebo twice daily (volume of injection equivalent to exenatide 5 µg or exenatide 10 µg). During the first 4 weeks after randomization, all patients assigned to treatment will receive exenatide 5 µg twice daily or equivalent placebo volume twice daily. A starting dose of exenatide 5 µg twice daily and titration to exenatide 10 µg twice daily has been shown to mitigate the incidence of nausea. At the end of 4 weeks post-randomization, patients assigned to the exenatide 10 µg twice daily treatment arm, or equivalent placebo volume, are then to increase their dose from 5 µg twice daily to 10 µg twice daily, or equivalent placebo volume. Study drug will be administered

[figure not shown]
within 60 minutes before morning and evening meals (or the 2 main meals of the day, approximately 6 hours or more apart) for 28 weeks.

All patients will be expected to participate in a simplified lifestyle modification program (LMP) throughout this study. The simplified lifestyle modification program will include both dietary education and physical activity components. At the clinic visits, the patients will meet with a registered dietitian (RD) or certified diabetes educator (CDE) who will review the patient's dietary history and physical activity record. The LMP will be reinforced at each visit.

Patients who have discontinued the study due to loss of glycemic control will be offered alternative antidiabetic therapy at the discretion of the investigator.

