4.1.1 Statistical notations and presentations

Although patients randomly assigned to placebo will be assigned to take the volume equivalent to 5 µg exenatide twice daily or to take the volume equivalent to 10 µg exenatide twice daily, all patients assigned to placebo will be combined into 1 group for analysis purposes. Descriptive summaries will present treatment groups separately, as follows:

5 µg EBID	10 µg EBID	Total EBID	Placebo	Total
EBID Exenatide twice daily				

Total EBID is the pool of the 10 µg and 5 µg EBID doses. Total (over all treatments) will not be included in efficacy and safety endpoint outputs.

Summaries including data from the safety follow-up period will be presented by the actual treatment group during the randomized period.

All efficacy and safety variables will be summarized using descriptive statistics as appropriate. Continuous variables will be summarized by descriptive statistics including n (number of patients with available data), arithmetic mean, standard deviation (SD), median, minimum value and maximum value. The mean and median will be presented with one more decimal place than the original data; the standard deviation with two more decimal places than the original data; and minimum and maximum values with the same number of decimal places as the original data. Categorical variables will be summarized using frequency tables (number of patients and percentage of patients in each category). Unless otherwise stated, percentages will be calculated out of the analysis set total for the treatment group. Percentages will be rounded to one decimal place.

For log transformed data, the following descriptive statistics will be presented: n (number of patients with available data), geometric mean, geometric coefficient of variation (GCV%), geometric standard deviation factor (GSD), arithmetic mean, standard deviation, coefficient of variation (CV%), median, minimum and maximum value.

GCV (%) will be calculated as

$$100 \cdot \sqrt{(\exp(s^2) - 1)}$$

where s is the SD of the data on a log scale.

Individual data will be presented in patient listings. All patient data listings will be sorted by treatment and patient identifier ID. The first 3 digits of the patient ID denotes the center number and the next 4 digits denotes the individual patient number.

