4.2.5 Safety analyses

4.2.5.1 Adverse events

Adverse events (AE) will be classified in accordance to the MedDRA dictionary. All adverse events will be coded using the latest available version of MedDRA by the database lock.

AEs starting (or worsening) after Week 28/ED but considered by the Investigator as clinically significant and as related to study medication or study procedure, and serious adverse events (SAE) occurring within 30 days of the last administration of study medication will be recorded on the AE CRF and reported in the AE listing.

Treatment-emergent AEs (TEAE) are defined as AEs starting (or worsening) after the first dose of study medication through the end of the treatment + 1 day (or + 30 days for SAEs and other clinically significant or related AEs), including AEs collected after patients initiate glycemic rescue therapy. For patients who discontinue study medication before Week 28, the end of the treatment refers to the date of the ED visit even if last study medication was before this date.

Adverse events with a start date prior to the first administration of study medication will be classified as pre-treatment (non-treatment emergent) and will be listed only.

Post-treatment AEs are defined as AEs that start (or worsen) during the off-treatment period (safety follow-up period) defined as the day after the Visit 11 (Week 28/ED) + 1 day (or + 30 days for SAEs and other clinically significant or related AEs) to the date of completion of the safety follow-up period. As per protocol only adverse events of special interest (AESIs) will be collected in long term extension.

On-treatment AEs (TEAEs) will be summarized for 28-week treatment period as defined below.

An overall summary of number and percentage of patients experiencing at least 1 TEAE will be presented for EBID and PBO. The AE summary will include the number and percentage of patients experiencing any AE, any SAE, any AE possibly related to study drug, study procedure or study device as judged by the investigator, any AE leading to treatment discontinuation, and any fatal AE.

Additionally, all TEAEs will be summarized for each treatment group as follows:

- AEs summarized by SOC, PT, intensity (Mild, Moderate, Severe), possibly related to study drug (No, Yes) and outcome
- SAEs summarized by SOC and PT, intensity (Mild, Moderate, Severe), possibly related to study drug (No, Yes)
- AEs leading to treatment discontinuation (DAE) summarized by SOC and PT

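### Read literally, SAP 2.1.5 puts 10 µg-arm patients who stop during the planned 5 µg initiation in the 5 µg safety column

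*SAP*

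**What the plan says.** SAP 2.1.5 sets the general rule: "Patients will be analyzed and presented in accordance to the actual treatment received, regardless of planned treatment assignment". For anyone who took at least one dose of exenatide it adds that "they will be analyzed and presented in accordance with the actual exenatide treatment received no matter what arm they were randomized to". It has one rule for patients exposed to both doses. That rule begins "If a patient randomized to the placebo arm receives exenatide at doses of both", goes on to name 5 µg and 10 µg, and sends such patients to the 10 µg group. It does not mention patients randomized to 10 µg.

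SAP 1.2 describes the initiation: "During the first 4 weeks after randomization, all patients assigned to treatment will receive exenatide" at 5 µg twice daily, or the matching placebo volume. The step-up comes afterwards: "At the end of 4 weeks post-randomization, patients assigned to the exenatide" 10 µg arm raise their dose. Protocol 6.1.3 and 8.5 describe the same scheme.

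On outputs, SAP 4.1.1 states: "Descriptive summaries will present treatment groups separately, as follows", and lists 5 µg EBID and 10 µg EBID as separate columns beside Total EBID and Placebo. SAP 4.2.5.1 states: "Additionally, all TEAEs will be summarized for each treatment group as follows", and its list includes adverse events leading to treatment discontinuation. SAP 4.2.3 summarizes exposure by treatment group on the Safety analysis set, in bands that start at 1-13 and 14-27 days.

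**The concern.** An actual-treatment rule normally handles patients given the wrong product. Here it also catches patients who followed their assigned regimen exactly but left before the step-up. Which column such a patient enters is then decided by something that happens after randomization, namely remaining on treatment for about 4 weeks.

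Both exenatide arms have the same planned dose in Weeks 0-4, so the expected difference between them in early adverse events is zero. A difference created by moving early leavers from one column to the other is an artefact of classification. It makes the 10 µg column look better tolerated and the 5 µg column worse.

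Protocol 4.1 says that nausea is "more frequent at the initiation of therapy", so the initiation period is a relevant window for tolerability. Protocol 5.2 lists comparison of the two doses with each other, safety and tolerability included, among the secondary objectives.

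**Working it through.** The plan gives no figure of its own on this point, so there is none to reproduce. The check has two steps.

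**1. Where the wording sends each kind of patient**

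- Randomized to 10 µg, stops before the step-up: has received 5 µg only, so goes to the 5 µg column under 2.1.5.
- Randomized to 10 µg, steps up: has received both doses. Section 2.1.5 names no column for this patient. By analogy with the placebo rule, the column is 10 µg.
- Randomized to 5 µg, stops at any time: 5 µg column.

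The analogy sorts by the highest dose received. It keeps patients who step up in the 10 µg column but still sends early leavers to 5 µg. Neither document says that the 10 µg treatment includes its initiation phase.

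**2. What this does to the columns**

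Inputs:

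- Arm size: SAP 1.3 gives 122 randomized at Total EBID:Placebo 2:1, and Protocol 8.3 gives equal exenatide arms, so N = 122/3 = 40.7, taken as 41 per arm.
- Early stops for adverse events, m per arm: not in the documents. Assumed 1, 2, 4 or 6, equal in both arms.
- Share a of the remaining patients with an adverse event in Weeks 0-4: not in the documents. Assumed 40%, varied from 20% to 50%.

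Discontinuation in Weeks 0-4 because of an adverse event:

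- as randomized: m/N in each arm
- literal rule: 2m/(N + m) for 5 µg and 0/(N − m) for 10 µg

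Any adverse event in Weeks 0-4, counting every early stopper as having one:

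- as randomized: [m + a(N − m)]/N in each arm
- literal rule: [2m + a(N − m)]/(N + m) for 5 µg and a for 10 µg

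| m per arm | Early AE stop, as randomized (both arms) | Literal rule, 5 µg | Literal rule, 10 µg | Any early AE at a = 40%, as randomized (both arms) | Literal rule, 5 µg | Literal rule, 10 µg |
|---|---|---|---|---|---|---|
| 1 | 1/41 = 2.4% | 2/42 = 4.8% | 0/40 | 41.5% | 42.9% | 40.0% |
| 2 | 2/41 = 4.9% | 4/43 = 9.3% | 0/39 | 42.9% | 45.6% | 40.0% |
| 4 | 4/41 = 9.8% | 8/45 = 17.8% | 0/37 | 45.9% | 50.7% | 40.0% |
| 6 | 6/41 = 14.6% | 12/47 = 25.5% | 0/35 | 48.8% | 55.3% | 40.0% |

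For m = 4 and a = 40%, the 5 µg entry is (8 + 0.4 × 37)/45 = 22.8/45 = 50.7%.

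The false difference in any early adverse event is 2.9 to 15.3 points at a = 40%, and 2.4 to 20.4 points over a from 20% to 50%. The 0% for 10 µg holds by construction. Total EBID stays at 2m/82 = m/41 under either classification. With m = 0 nothing moves.

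Exposure shows the same mechanism. A patient must reach the step-up at about Week 4 to enter the 10 µg column, so that column's 1-13 day band is empty unless someone stepped up early in error.

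**The case against.** The best counter-argument is that treatment in 2.1.5 means the assigned regimen. SAP 1.2 describes the 10 µg arm as 5 µg for 4 weeks and then a step-up, so a 10 µg-arm patient taking 5 µg in Week 2 is receiving exactly what was assigned, and planned and actual treatment agree. The dose reading also leaves every 10 µg-arm patient who steps up without a stated column, which the authors are unlikely to have wanted. This is plausible, and it means that the literal outcome may not have been intended. But the regimen reading is written nowhere, the only both-doses rule sorts by dose received, and two programmers could build different tables from the same text.

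A second argument is that the disposition table would expose the shift. SAP 4.2.1.1 tabulates early discontinuation with reasons, using ITT denominators, and SAP 2.1.2 analyzes ITT patients by planned group. So the stops remain visible under the randomized arm. That is a useful cross-check, but it does not correct the columns for treatment-emergent events, events leading to discontinuation, or exposure.

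Third, the size is assumed. SAP 1.3 gives about 23% discontinuation in the exenatide arms overall, or 0.23 × 41 = 9.4 patients per arm, with no Week 0-4 share. Four early stops would be 4/9.4 = 42% of that total, and six would be 64%. This stands: the upper rows of the table need strong clustering in the first 4 of 28 weeks.

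Some stronger readings are tempting but unsupported:

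- A reader might infer that nausea peaks at initiation and drives early stopping. Protocol 4.1 says only that it is more frequent then, calls it mild or moderate, and does not link it to discontinuation.
- A reader might treat the safety columns as the plan's main evidence on dose. The SAP does not say so. Efficacy summaries also show both doses, by planned group, and SAP 4.2.4.3 adds a sensitivity analysis of the active doses against placebo.

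**Conclusion.** The point holds as a matter of wording. Taken literally, SAP 2.1.5 classifies 10 µg-arm early leavers as 5 µg patients, which makes the dose column depend on a post-randomization outcome. Confidence that the text permits this is high; confidence that the authors meant it is not.

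The direction is fixed: it favours 10 µg and disfavours 5 µg in the early safety data. The size is unknown. The illustrated range rests on 41 patients per arm, equal early stops in the two arms, and 1 to 6 such stops; the distortion grows with their number.

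The reach is limited to the descriptive 5 µg and 10 µg safety columns. It would be wrong to infer that the comparison with placebo or the efficacy conclusions are biased. Pooling the two doses cancels the shift, and SAP 2.1.3 and 2.1.4 analyze efficacy by planned group.

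**What to change.** Add to SAP 2.1.5, before unblinding (SAP 4.1 already requires patients to be assigned to analysis sets by then):

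- For patients randomized to 10 µg, the treatment is the regimen including its planned 5 µg initiation. Those who stop before the step-up are presented in the 10 µg group. This also gives a stated column to patients who do step up and so receive both doses.
- The actual-treatment rule continues to apply to any patient who received a product or dose other than the one planned for their arm at that time. This includes an exenatide-randomized patient given only placebo. A narrower exception, limited to exenatide given to placebo patients or 10 µg given to 5 µg patients, would leave that patient in an exenatide column.

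The cost is a sentence or two of SAP text and the matching derivation of the treatment variable. No data collection, dosing or efficacy analysis changes.

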2.1.6 Safety follow-up analysis set

The safety follow-up (SFU) analysis set consists of all patients who have at least 1 safety follow-up period assessment Visit 801 (6 months after Week 28/ED) to Visit 806 (3 years after Week 28/ED).

This set will be used for listings and summaries of safety data during the safety follow-up period.

2.1.7 Pharmacokinetic (PK) analysis set

The PK analysis set will consist of all patients who receive at least 1 dose of EBID, for whom at least 1 evaluable post-dose PK concentration assessment is available, and do not deviate from the clinical study protocol (CSP) in ways that would significantly affect the PK analyses, as determined at the final protocol deviations meeting prior to unblinding of this study. Patients will be presented in accordance to the actual treatment received.

This set will be used for listing of PK data.

2.2 Violations and deviations

AstraZeneca use ICH E3 terminology for protocol deviations (PD), which are all important deviations related to study inclusion or exclusion criteria, conduct of the trial, patient management or patient assessment.

Important deviations may include deviations pertaining (but not limited) to those presented in Table 1.

These protocol deviations will be programmatically derived (where possible) and presented in a listing. In addition, protocol deviations attributed to these criteria reported in the IQVIA Clinical Trial Management System (CTMS) for all patients randomized by IQVIA in this study will be reported in the Clinical Study Report (CSR). No additional per protocol analyses are planned.

Table 1 Important Protocol Deviations

Number	Important protocol deviations criteria
1	Randomized patients without type 2 diabetes or central laboratory HbA1c obtained at screening not within $\pm 0.2\%$ of the protocol-specified HbA1c range
2	Randomized patients not satisfying the target population baseline antihyperglycemic therapy requirement
3	Randomized patients who were treated with any systemic corticosteroid therapy for ≥ 5 consecutive days during randomized treatment
4	Randomized patients who received no (or incorrect) study medication at any time during the 28-week treatment period (*).
5	Patients assigned to the incorrect IVRS randomization stratification factor as compared to the HbA1c test result at screening ($\leq 8.0\%$ or $> 8.0\%$) or background diabetes therapy (drug naïve, metformin only, SU only and metformin + SU)
6	Missed the background anti-diabetic medication for ≥ 10 consecutive days in the last three months of the study (*)
7	No valid baseline HbA1c
8	No single valid on-treatment HbA1c
9	Randomized patients who are not compliant with study medication administration requirements (dose, frequency) (*)

(*) PD will only be presented from the CTMS as not possible to fully identify programmatically.

This list is not intended to be all-inclusive. Other protocol deviations may be identified by the study team during on-going review of the study conduct prior to treatment unblinding.

3 PRIMARY AND SECONDARY VARIABLES

3.1 Primary efficacy variable

The primary efficacy endpoint for the treatment period is the change in HbA1c from baseline Visit 3 (Week 0) to Visit 11 (Week 28).

3.2 Secondary efficacy variables

The following are the secondary efficacy endpoints:

- Change in HbA1c from baseline Visit 3 (Week 0) to each intermediate visit as applicable

- Proportion of patient achieving HbA1c goals of <7%, ≤6.5%, and <6.5% at Visit 11 (Week 28) and each intermediate visit as applicable
- Change in body weight from baseline Visit 3 (Week 0) to Visit 11 (Week 28), and to each intermediate visit as applicable
- Change in FSG from baseline Visit 3 (Week 0) to Visit 11 (Week 28)
- Change in FSI from baseline Visit 3 (Week 0) to Visit 11 (Week 28)
- Change in SMBG measurements before and 2 hours after the 2 main meals of the day on 3 days during the week before Visit 3 (Week 0) and Visit 11 (Week 28)
- Change in HOMA-B and HOMA-S as measured by homeostasis model assessment from baseline Visit 3 (Week 0) to Visit 11 (Week 28)
- Proportions of patients discontinuing the study, due to failure to maintain glycemic control at Visit 11 (Week 28), and to each intermediate visit as applicable

3.3 Exploratory efficacy variables

The exploratory efficacy endpoints are:

- Change in body mass index (BMI) from baseline Visit 3 (Week 0) to Visit 11 (Week 28), and to each intermediate visit as applicable
- Change in body weight and BMI percentile from baseline Visit 3 (Week 0) to Visit 11 (Week 28), and to each intermediate visit as applicable. The body weight and BMI percentiles will be determined based on the standardized growth chart for boys and girls (2000 CDC Growth Charts)
- Change in hip and waist circumference from baseline Visit 3 (Week 0) to Visit 11 (Week 28)

